#### Table 3: Laboratory Values Defining Adequate Organ Function

Abbreviations: ALT=alanine aminotransferase; ANC=absolute neutrophil count; aPTT=activated partial thromboplastin time; AST=aspartate aminotransferase; CrCl=creatinine clearance; INR=international normalized ratio; PT=prothrombin time; ULN=upper limit of normal

a CrCl should be calculated per institutional standard.

- 12. Female patients of childbearing potential should have a negative urine or serum pregnancy test within 72 hours prior to receiving the first dose of study medication. If the urine test is positive or cannot be confirmed as negative, a serum pregnancy test will be required.
- 13. Is willing to abide by the contraception requirements for the duration of the study (additional details regarding contraception requirements are provided in Section 8.4.1).

## 7.2. Patient Exclusion Criteria

- 1. Has a diagnosis of immunodeficiency or is receiving systemic steroid therapy (inhaled or topical steroids are allowable) or any other form of immunosuppressive therapy within 7 days prior to the first dose of study drug.
- 2. Has active tuberculosis (TB; *Bacillus tuberculosis*).
- 3. Has hypersensitivity to pembrolizumab, ALKS 4230, or any of their excipients.
- 4. Has prior Grade ≥3 immune-related toxicities requiring systemic immunosuppressant treatment that were attributable or possibly attributable to PD-1 immune checkpoint blockade. Has toxicities deemed reversible from prior therapy, including anti-PD-1, that have not recovered to baseline or Grade ≤1. Patients with persistent Grade ≤2 neuropathy are an exception to this criterion and may qualify for the study.
  - a. **Note**: If patient received major surgery, the patient must have recovered adequately from the toxicity and/or complications from the intervention prior to starting therapy.
- 5. Has had a prior dose of anti-PD-(L)1 therapy within 3 weeks of Study Day 1, with the exception of an anti-PD-(L)1 inhibitor that is dosed Q2W and in consultation with the ION and Alkermes Medical Monitors.
- 6. Has a known history of additional malignancy within 2 years or current additional malignancy that is progressing or requires active treatment. Exceptions include basal cell carcinoma of the skin or squamous cell carcinoma of the skin that has undergone potentially curative therapy, in situ cervical cancer, or treated prostate cancer with a prostate-specific antigen value of <0.01 ng/mL.
- 7. Has known active central nervous system (CNS) metastases and/or carcinomatous meningitis. Patients with previously treated brain metastases may participate, provided that they are stable (without evidence of progression by imaging for at least 4 weeks prior to the first dose of study drug and any neurologic symptoms have returned to baseline), have no evidence of new or enlarging brain metastases, and are not using steroids for at least 7 days prior to study drug. This exception does not include carcinomatous meningitis, which is excluded regardless of clinical stability.
- 8. Has known history of, or any evidence of, non-infectious interstitial pneumonitis that required steroids or current pneumonitis, or oxygen requirement for any reason in the past 28 days.
- 9. Has an active major infection requiring systemic therapy within 1 week of starting study drug.

- 10. Has a history or current evidence of any condition, therapy, or laboratory abnormality that might confound the results of the study, interfere with the patient's participation for the full duration of the study, or is not in the best interest of the patient to participate, in the opinion of the treating Investigator.
- 11. Has known psychiatric or substance abuse disorders or a social situation that would interfere with cooperation with the requirements of the study.
- 12. Is pregnant or breastfeeding or expecting to conceive or father children within the projected duration of the study, starting with the Screening Visit through 120 days after the last dose of study drug (see Section 8.4.1 for additional details).
- 13. Known active infection with hepatitis B (hepatitis B surface antigen [HBsAg] reactive) or hepatitis C (hepatitis C virus [HCV] RNA [qualitative]) detected.
- 14. Has any finding that, in the view of the Investigator, would compromise the safety of the patient or affect their ability to adhere to the protocol visit schedule or fulfill visit requirements.
- 15. Is Investigator-site personnel, an immediate family of the Investigator-site personnel, employed by Alkermes or ION, or an immediate family member of an Alkermes or ION employee.
- 16. If, in the opinion of the Investigator (and/or Sponsor), the patient is unsuitable for enrollment in the study.
- 17. Has significant known cardiovascular impairment (New York Heart Association Congestive Heart Failure >Grade 2, unstable angina, myocardial infarction within the previous 6 months prior to the first dose of investigational drug, or existing serious cardiac arrhythmia).
- 18. Has chronic or acute gastrointestinal (GI) disorders resulting in diarrhea of any severity grade; patient is using chronic anti-diarrheal supportive care (more than 3 days/week) to control diarrhea in the 28 days prior to the first dose of investigational drug.
- 19. Has known cirrhosis diagnosed with Child-Pugh Class A or higher liver disease.

## 7.3. Patient Withdrawal and Discontinuation

A patient may be discontinued from the study at any time if the patient or Investigator determines that it is not in the best interest of the patient to continue participation. Reasons for discontinuation include:

- Adverse event (see Section 12.1.)
- Disease progression
  - For unconfirmed radiographic disease, see Section 8.3.10.
  - A patient may be granted an exception to continue on treatment with confirmed radiographic progression if the patient is clinically stable and upon written agreement from both ION and Alkermes Medical Monitors (see Section 8.3.10).
- Intercurrent illness that prevents further administration of treatment

- The need for administration of an excluded or prohibited medication
- Loss to follow-up
- Withdrawal of consent
- Non-compliance with study drug
- Physician decision
- Pregnancy
- Protocol deviation
- Study terminated by Sponsor
- Other

If a patient withdraws from the study for any reason, any ongoing adverse events (AEs) will be followed until resolution, until deemed stable by the Investigator, until initiation of new anticancer therapy, or until the patient is deemed by the Investigator to be lost to follow-up. If, in the opinion of the Investigator, it is necessary to monitor a patient beyond the Safety Follow-up Visit, the follow-up period may be extended as necessary. In such instances, the Sponsor and the Investigator will agree to an acceptable follow-up schedule.

In the event that a patient chooses to withdraw from the study, the Investigator should make a reasonable effort to ascertain the reason(s) for withdrawal, while fully respecting the patient's rights. Enrolled patients are to be asked to return to the clinic for an End of Treatment (EOT) Visit. The EOT Visit should be scheduled as close as possible to the patient's last dose, and early termination assessments will follow the assessments scheduled to be conducted at the EOT Visit. If the patient fails or refuses to return to the study center, an attempt must be made to contact the patient by telephone in order to assess as many safety and efficacy parameters as possible. All data collected over the telephone must be documented and kept in the patient's study record.

The Investigator must maintain a record of all patients who fail to complete the study. The reason for study discontinuation will be documented and made on the appropriate electronic case report form (eCRF). If a patient is lost to follow-up, a reasonable attempt to contact the patient must be made and documented.

The Sponsor reserves the right to terminate the study at any time for any reason.

## 7.3.1. Discontinuation of Study Drug After Complete Remission

## 7.4. Replacement of Patients

Patients who do not receive all doses of ALKS 4230 and pembrolizumab in Cycle 1 will be replaced, unless they missed a dose due to toxicity, as assessed by the Investigator. Patients who miss a dose of ALKS 4230 and pembrolizumab in Cycle 1 due to toxicity will not be replaced.

Patients who do not provide a second biopsy may be replaced at the discretion of the Investigator.

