#### 5.3.2. ALKS 4230

All patients in this study will be given ALKS 4230 at a daily dose of 3  $\mu$ g/kg for 5 consecutive days on Days 1 through 5 of the first week of each 3-week treatment cycle.

A first-in-human (FIH) clinical study with ALKS 4230 has been initiated and is currently ongoing (ALK4230-A101). This study is being conducted in patients with advanced solid tumors who are refractory or intolerant to therapies known to provide clinical benefit. Patients are administered ALKS 4230 by a 30-minute intravenous (IV) infusion daily for 5 days followed by an off-treatment period (as described in the ALK4230-A101 protocol) in repeating cycles. Dosing is repeated every 21 days, except during the first treatment cycle, which is 14 days.

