- v The post-treatment (second) biopsy will be performed on the same or similar tumor site during the first cycle of therapy at C1D12, or at any time from C1D8 through C1D19.
- w Fecal swab/storage devices and instructions must be given to the patient; sample collection to be performed at home by patient and returned to clinical research site at the next study visit.
- x Additional information regarding correlative studies is located in Table 16, and additional instructions are provided in the Laboratory Manual.

Patient Group	Imaging	Follow-up	AE Tracking
Patients with SD/PR who continue on Tx, no progression, for up to 1 year	9 weeks post-treatment start (within 7 days prior to Cycle 4), then within 7 days prior to every 3 rd cycle Follow-up: every 12 weeks ±1 week	Safety Follow-up Visit at 30 days after discontinuation Clinic visit every 8 weeks	Until 90 days after discontinuation or 30 days after discontinuation if patient begins new anticancer therapy
Patients who progress on-study before 1 year	Per local standard of care	Safety Follow-up Visit at 30 days after discontinuation or before start of new therapy, if applicable (in- clinic) Safety Follow-up Visit at 90 days after discontinuation (in-clinic preferable, by phone possible) Survival telephone call every 12 weeks for up to 2 years	Until 90 days after discontinuation or 30 days after discontinuation if patient begins new anticancer therapy
Patients who discontinue treatment due to any reason other than progression	Per local standard of care or Investigator clinical judgment	Safety Follow-up Visit at 30 days after discontinuation or before start of new therapy, if applicable Clinic follow-up until toxicity resolves or until death	Until 90 days after discontinuation or 30 days after discontinuation if patient begins new anticancer therapy
Patients who achieve CR on Tx (after at least 24 weeks of Tx + 2 doses post-CR imaging)	After discontinuation of treatment: Follow-up: every 12 weeks ±1 week OR at clinical signs/symptoms of progression	Safety Follow-up Visit at 30 days after discontinuation Clinic visit every 8 weeks	Until 90 days after discontinuation or 30 days after discontinuation if patient begins new anticancer therapy

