#### 8.3.10.1. Definitions

Evaluable for toxicity: All patients will be evaluable for toxicity from the time of consent.

Evaluable for objective response: Only those patients who have measurable disease present at baseline, have received at least one cycle of therapy, and have had their disease re-evaluated will be considered evaluable for response. These patients will have their response classified according to the definitions stated below. (NOTE: Patients who exhibit objective disease progression prior to the end of Cycle 1 will also be considered evaluable.)

Evaluable Non-Target Disease Response: Patients who have lesions present at baseline that are evaluable but do not meet the definitions of measurable disease, have received at least one cycle of therapy, and have had their disease re-evaluated will be considered evaluable for non-target disease. The response assessment will be based on the presence, absence, or unequivocal progression of the lesions.

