## **13. STATISTICS**

#### **13.1.** Sample Size Considerations

This study plans to enroll efficacy evaluable patients in Groups 1 and 2,

In the long-term follow-up analysis of the KEYNOTE-012 trial of single agent pembrolizumab, which was conducted in 192 patients with HNSCC, the objective improvement rate was 18% (95% CI, 13% to 24%) (Mehra et al, 2018). Among the subset of patients achieving a response, the median time to objective improvement was 2 months (range, 2 to 17 months).

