#### **13.2.1.** Study Populations

#### **13.2.1.1.** Efficacy Evaluable Population

All patients who received at least 1 dose of both study drugs will be included in the analysis of efficacy, regardless of the duration of treatment. The Efficacy Evaluable populations will be characterized by groups (Group 1 and Group 2) and overall for analysis of all efficacy endpoints.

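### Neither document says whether replaced patients stay in the primary analysis, and the SAP's scan requirement drops dosed patients who fail before the first scan

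*Protocol*

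**What the plan says.** Protocol 7.4 has two replacement rules. The first is mandatory: "Patients who do not receive all doses of ALKS 4230 and pembrolizumab in Cycle 1 will be replaced". Toxicity, as judged by the Investigator, is the one exception. The second is optional: "Patients who do not provide a second biopsy may be replaced at the discretion of the Investigator". It requires no reason and sets no deadline. Section 7.4 does not say what becomes of the replaced patient's data.

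Three passages define who counts for efficacy:

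- Protocol 13.2.1.1, the set that 13.4.1 names for the primary analysis, takes everyone with at least one dose of each drug; they "will be included in the analysis of efficacy, regardless of the duration of treatment".
- Protocol 8.3.10.1 asks for one cycle and a re-evaluation before a patient is evaluable for response, but adds that "Patients who exhibit objective disease progression prior to the end of Cycle 1 will also be considered evaluable".
- SAP 3.2.1 starts from the protocol set and adds at least one scan after baseline. SAP 5.1 lists this openly as a revised definition.

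Protocol 13.4.2, under the secondary analyses, treats patients with missing response data as non-responders. The SAP does not repeat that rule and does not mention replacement. Its primary-rate formula in 3.11.2 divides by the number of patients in the group, within the Efficacy Evaluable set. Protocol 13.1 frames enrolment in the same terms: "This study plans to enroll efficacy evaluable patients in Groups 1 and 2". The planned number is blanked in the public text and is not treated here as missing.

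**The concern.** The primary result is a single-arm response rate, so it depends directly on who is in the denominator. Patients who die, deteriorate or withdraw before the first scan are almost all non-responders. If they leave the denominator and new patients take their places, the rate describes patients who reached a scan. The stated objective is the rate in patients treated with the combination.

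The documents leave this open in two ways. The silence on replaced patients means that two programmers could build different primary sets. Separately, the SAP's scan condition removes unscanned patients whom the protocol would keep as non-responders. The biopsy rule raises a further issue. The study is open-label, response is read locally, and no deadline is set, so the decision to add a patient could be taken after the week-6 result is known.

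**Working it through.** **1. Timing.** ALKS 4230 is given on "consecutive days on Days 1 through 5 of the first week of each 3-week treatment cycle" (Protocol 5.3.2) and pembrolizumab on Day 1 (9.1.2), so the dosing trigger concerns doses due by about Day 5. The second biopsy is due "at C1D12, or at any time from C1D8 through C1D19" (Table 4 footnotes). The first on-study scan is at 6 weeks ± 7 days (8.3.10 and Table 4). Tables 5 and 7 give 9 weeks and need reconciling; I use week 6, the earlier.

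**2. Each rule applied to typical patients, all given at least one dose of each drug.**

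| Patient | Replaced under 7.4? | Protocol 13.2.1.1 | SAP 3.2.1 |
|---|---|---|---|
| Stops on Day 3, not for toxicity, never scanned | Yes | In | Out |
| Full Cycle 1 dosing, no biopsy, withdraws before any scan | At discretion | In | Out |
| Full Cycle 1 dosing, biopsied, dies before any scan | No | In | Out |
| Misses a Cycle 1 dose for toxicity, biopsied, never scanned | No | In | Out |
| Misses a Cycle 1 dose, not for toxicity, scanned | Yes | In | In |
| Full Cycle 1 dosing, no biopsy, scanned | At discretion | In | In |

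Replacement status does not decide membership of either set; the scan condition does. Section 7.4 refills the first row and possibly the second.

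**3. Plan's own figures.** No sample size, null rate, target rate or power is visible, so there is no design figure to reproduce. The benchmark in 13.1 is coherent: 35/192 = 18.2% with an exact 95% interval of 13.0% to 24.4%, and 34/192 = 17.7% (12.6% to 23.9%). Both round to the stated 18% (13% to 24%).

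**4. Effect on the rate.** Let p be the rate in all dosed patients and r the share lost, all non-responders. The expected rate in those left is p/(1 − r). With p = 18% for illustration:

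- r = 5%: 0.18/0.95 = 18.9%
- r = 10%: 0.18/0.90 = 20.0%
- r = 15%: 0.18/0.85 = 21.2%
- r = 20%: 0.18/0.80 = 22.5%

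If all dosed patients stay in, the expected rate remains p however many are replaced. A small case: 4 responders in 20 counted patients, after 2 early failures are dropped and refilled, is 20.0% (5.7% to 43.7%). With both kept it is 4/22 = 18.2% (5.2% to 40.3%).

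**5. How large r might be.** The documents give no value. As a crude marker, take the median survival of 6 to 9 months in Protocol 5.1, a constant hazard, and deaths by day d = 1 − 0.5^(d/30.4/median).

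- Day 5 (dosing trigger): 1.3% to 1.9%, which moves 18% to 0.18/0.987 = 18.2% or 0.18/0.981 = 18.3%.
- Day 19 (end of biopsy window): about 5% to 7%.
- Day 42 (first scan): 1 − 0.5^(42/30.4/9) = 10.1% to 1 − 0.5^(42/30.4/6) = 14.8%.

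Eligibility (ECOG 2 or less, adequate organ function) and the SD and PR patients in Group 1 should make early deaths fewer than this. Withdrawal and deterioration without a scan would add to them.

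**6. Effect on a test.** SAP 3.11.2 plans an exact binomial test with no visible null rate. Assume a null of 18%, an upper tail of 0.025 and a true all-dosed rate of 18%. The chance of rejecting at r = 0, 10% and 20% is 0.018, 0.032 and 0.060 for N = 20 (8 or more responses); 0.012, 0.026 and 0.056 for N = 30 (11 or more); and 0.020, 0.043 and 0.096 for N = 40 (13 or more). N and the null are assumptions.

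**The case against.** A reader might infer more from 7.4: that it conflicts with the evaluable-population rules and lets an Investigator swap early failures out of the primary rate at any time. The documents do not support that reading.

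- Section 7.4 says replaced; it never says excluded. Under 13.2.1.1 a replacement only adds a patient. Inferring removal from the enrolment target would mean reading intent into a sentence whose number is blanked.
- No deadline is stated for biopsy replacement, which is weaker than a licence to act at any time.
- The dosing trigger is narrow. A patient who progresses on Days 6 to 21 after full dosing does not meet it, and it acts about five weeks before the first scheduled scan, so a known response can hardly drive it.
- The main rule of 8.3.10.1, one cycle and a re-evaluation, points partly the same way as 7.4 and the SAP. Only its note on early progressors pulls the other way.

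There are also safeguards. The second biopsy is mandatory and may be bypassed only for safety after discussion with the Sponsor (8.3.12.1). SAP 3.3 tabulates the Safety and Efficacy Evaluable sets and the reasons for discontinuation, so the number dosed but not scanned could largely be worked out. No interim analysis is planned.

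All of this stands, and it limits what can be said about 7.4. It does not answer the SAP's scan condition, which removes dosed, unscanned patients by definition. Being disclosed in SAP 5.1 does not make that condition consistent with 13.2.1.1 or 13.4.2. Nor do the safeguards say how replaced patients are to be analysed or reported.

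**Conclusion.** The point holds as a gap in 7.4 combined with a denominator problem in the SAP. Neither document gives the analysis status of replaced patients. The protocol's primary set keeps them. The SAP's set drops any dosed patient without a scan, replaced or not, and 7.4 refills some of those places. The loss runs one way where those dropped are non-responders.

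The size rests on r, which is assumed: 18% becomes 18.9% at 5% and 20.0% at 10%. The Cycle 1 dosing trigger alone probably accounts for only a few percent; most of any inflation would come from the scan condition acting up to week 6. For a study of modest size this shift is well inside the confidence interval, but it is systematic and avoidable.

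The biopsy rule is a lesser matter. A scanned patient without a biopsy stays in both sets, so what remains is that the timing of an added patient could depend on a known outcome. I have put no size on that.

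**What to change.** 1. In Protocol 7.4 and SAP 3.2.1, state that replacement adds a patient and never removes one.
2. For the primary rate, remove the scan condition from SAP 3.2.1 and 5.1. Every patient with at least one dose of each drug stays in the denominator and counts as a non-responder if response is not assessed. The scan-required set can be kept as a sensitivity analysis.
3. Require that any replacement for a missing biopsy be decided before that patient's week-6 scan is read.
4. In the SAP 3.3 disposition table, list replaced patients by group with the reason.

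This takes one protocol clarification and a short SAP edit that reverses the revision in 5.1. The number analysed may slightly exceed the target, and the reported rate may be slightly lower. Nothing about treatment changes.

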## 8. STUDY DESIGN

#### 8.1. Overall Study Design and Plan

The study will assess the antitumor efficacy of ALKS 4230 in combination with pembrolizumab in patients with advanced, recurrent, and/or HNSCC on treatment with an anti-PD-(L)1 antibody (pembrolizumab or nivolumab) without having achieved a CR.

The study is a multi-center, Phase 2, open-label therapy study in collaboration with ION. Patients must have received anti-PD-(L)1 therapy prior to enrollment into the study. After enrollment in the study, ALKS 4230 with pembrolizumab will be administered to 4 cohorts of patients with advanced, recurrent, and/or metastatic HNSCC who have received anti-PD-(L)1 therapy whose current response is as follows:

- Cohort 1: SD, defined as  $\geq 12$  weeks of SD per RECIST criteria;
- Cohort 2: PR with no further reduction in tumor size or response for ≥8 weeks (ie, PR and not improving further)
- Cohort 3: PD with no prior response to anti-PD-(L)1 therapy after ≥8 weeks on anti-PD-(L)1, or
- Cohort 4: Current PD after prior achievement of best response of SD or PR and after ≥8 weeks on anti-PD-(L)1 therapy

Patients will be administered the combination of ALKS 4230 and pembrolizumab. For simplification, the 4 cohorts of patients will be combined into 2 arms:

- Group 1 will consist of all patients with current SD or PR (Cohorts 1 and 2) who are not progressing or further demonstrating reductions in tumor size.
- Group 2 will consist of patients with PD (Cohorts 3 and 4).

Baseline tumor biopsy will be required at the time of study entry after screening procedures have been completed and prior to first administration of combination regimen to assess each patient's tumor characteristics in an effort to identify patients with tumors that may have limited pembrolizumab efficacy or potential response to anti-PD-1/ALKS 4230 combination. Tumors will be assessed for quantity and character of tumor-infiltrating T cells and other leukocytes, and for quantitative assessment of PD-L1 expression, gene signatures that correlate with response or lack of response

Patients will also have a post-treatment (second) biopsy at C1D12, or at any time from C1D8 through C1D19, to assess whether the addition of ALKS 4230 to the treatment regimen alters the TME and what changes on therapy (immunopharmacodynamics) predispose to responses to the combination.

The study plans to enroll **and a construction** evaluable patients for Groups 1 and 2, **and a construction** The number of patients enrolled into each cohort within each group will be determined at the time of enrollment, based on the patient's response to previous treatment It will be at the discretion of

Alkermes and ION to expand a particular cohort of interest

Pembrolizumab will be administered according to the standard regimen of 200 mg flat dose IV Q3W. ALKS 4230 will be administered IV at a daily dose of 3  $\mu$ g/kg, given daily on 5 consecutive days on Days 1 through 5 of the first week of each 3-week treatment cycle.

ALKS 4230 may be continued until toxicity develops. If a toxicity attributed to ALKS 4230 occurs, dosing for both pembrolizumab and ALKS 4230 will be held. After recovery from an AE that meets dose hold criteria, the patient may resume at full dose of pembrolizumab and full or reduced dose of ALKS 4230 in subsequent cycles with consultation from the Medical Monitor or may discontinue from the study.

